Serum uric acid level will be drawn at the baseline visit given evidence suggesting that there may be an inverse relationship between levels of uric acid and rate of PD progression^{7,8}. Uric acid level is for research purposes only.

The PI or co-investigator will once again review the inclusion/exclusion checklist at the time of the baseline visit.

D5. d. Treatment assignment & administration

For subjects meeting enrollment criteria and providing consent, treatment with H₂-enriched water or placebo will begin after the baseline visit. The subject will be randomly assigned to either the active treatment or the placebo group. A blocked randomization list will be generated using the following website: <https://www.sealedenvelope.com/simple-randomiser/v1/lists>. The research pharmacist will be responsible for using the generated list to assign treatment to subjects as they are enrolled. The study staff assessing study outcomes will remain blinded to treatment assignment. The study doctor will dispense study drug to the subject. Masking of active and placebo treatment will be maintained by bottling tablets in containers that appear identical.

The medication will be administered orally as 250 mL BID of H₂-enriched or placebo drinking water. Subjects will be instructed to adhere to a q6h – q10h schedule, but for convenience a dose may be taken a few hours earlier or later, as there is no expected mechanism of action indicating that dose timing would be critical for efficacy.

D5. e. Follow-up visits

Follow-up visits will be scheduled to occur at weeks 8, 24, 40, 52, and 56 (\pm 4 weeks). Adverse effects will be monitored to assess safety and tolerability in this patient population. The study doctor will dispense study drug to patient at weeks 8, 24, and 40. The subject will be counseled to call the investigator immediately to report the occurrence of any adverse events. Subjects will be instructed to return bottles with unused tablets at each follow-up visit. Tablet counts will be performed by the research pharmacist to monitor patient compliance.

As a temporary measure to allow for continuity of this study during the COVID-19 pandemic, follow-up visits will be conducted remotely via telephone and/or secure videoconferencing using

the Microsoft Teams application. The following modifications will be made to follow-up visits during this time period:

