At the time of the baseline visit, subjects will be provided with H₂ tablets (or placebo tablets) to take home with them. Subjects will be instructed to twice a day dissolve one tablet in 250 mL (8 ounces) of drinking water and then drink the entire glass of effervescent water. Subjects who cannot tolerate thin liquids can use commercial pre-thickened water or commercial thickener to achieve the tolerated consistency (ie. nectar-thick or honey-thick).

Subjects will be instructed to adhere to a roughly q6h – q10h schedule, but for convenience a dose may be taken a few hours earlier or later, as there is no expected mechanism of action indicating that dose timing would be critical for efficacy.

Subjects who are taking routine dietary magnesium supplementation will be advised to suspend this supplementation for the duration of the study, given the presence of magnesium in the H₂ tablets and placebo.

Justification of Dosage

Fu and colleagues found that *ad libitum* administration of 50% saturated H₂-enriched drinking water reduced nigral dopaminergic cell loss in a rat PD model¹¹. Furthermore, a recent small pilot trial involving a total of 17 patients with idiopathic PD demonstrated that drinking 1000

mL/day of H₂-enriched water was well-tolerated in PD patients, with possible positive effect on motor symptoms¹⁴.

For these reasons, we have selected a dosage target of 250 mL BID of H₂-enriched drinking water. Duration of therapy is set at 52 weeks.

D7a. Primary Outcome Measures

1. **Safety:** To investigate the safety of H₂-enriched water in PD patients. Safety is defined as the absence of serious adverse events (SAEs) warranting termination of the treatment arm or the trial, as determined by the Data and Safety Monitor.
2. **Tolerability:** To investigate the tolerability of H₂-enriched water in PD patients. Tolerability is defined as the extent to which the treatment group can continue without prolonged treatment suspension (>24 consecutive days or >36 cumulative days) due to adverse events (AEs), as assessed 24 and 52 weeks after receiving the study drug.

The criteria for monitoring safety and tolerability have been modeled after previous phase II clinical trials of antioxidant use in early stage PD patients⁹.

D7b. Secondary Outcome Measures

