The primary objective of this study will be to assess the safety and tolerability of H₂-enriched water in patients with PD. Safety will be assessed by comparing time to first SAE by log-rank tests. As noted above, safety is defined as the absence of serious adverse events (SAEs) warranting termination of the treatment arm or the trial, as determined by the Data and Safety Monitor. Tolerability will be defined as the extent to which the treatment group can continue without prolonged treatment suspension (>24 consecutive days or >36 cumulative days) due to adverse events (AEs), as assessed 24 and 52 weeks after receiving the study drug. The study is reasonably powered to detect the emergence of an SAE; of note, there were no adverse events or drop-outs in the active treatment arm of a prior pilot study including 9 patients on active treatment with H₂-enriched water¹³.

We also plan to perform an exploratory analysis looking for evidence of benefit against disease progression in PD using the secondary outcome measures described above (see D7b). In order to obtain meaningful results towards this end, we have therefore powered the study to detect a superiority of treatment with H₂-enriched water compared to placebo in slowing PD disease progression. A prior pilot study demonstrated changes in the motor subscale of the UPDRS (UPDRS-III) that trended towards significance when comparing active treatment with H₂-enriched water to placebo (-5.7 ± 8.4 vs. 4.1 ± 9.2 for active treatment vs. placebo, respectively). Power calculation using this data suggests that a sample size of 60 will be sufficient to detect a between-group difference with a 2-sided $\alpha = 0.01$ and power = 90%. We plan on a sample size of 70 to account for drop-outs who voluntarily discontinue study treatment and study visits, and are therefore lost to follow-up.

F. FUNDING STATUS, DETAILS

This is an investigator-initiated study that will be funded at launch from the investigators' own uncommitted research funds, possibly with assistance from the Department of Neurology. The investigators may seek outside funding if interim results are encouraging.

G. HUMAN SUBJECTS RESEARCH PROTECTION FROM RISK

G 1. Risk to Subjects

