The PI and all key personnel involved in the study will have completed the Collaborative IRB training initiative and HIPAA training. The PI will be responsible for reporting adverse events experienced by study subjects to the IRB according to IRB guidelines.

Confidentiality will be maintained. All subject research data will be coded with subject ID number. Paper files will be kept in a secure, locked area. The electronic database used during the study will be secured with a password and saved on a secured shared drive only accessible to key

personnel. Subject results will never be discussed in any form in the presence of other subjects in the study, or with non-laboratory personnel. Subjects' names will not be used in manuscripts or presentations about this research.

G3. Potential Benefits of Proposed Research to the Subject and Others

The proposed therapy may slow the progression of Parkinson's disease, a common neurodegenerative disorder for which disease-modifying treatment is not currently available. Even if the study is negative, observations made during the study may aid the development of future neuroprotective trials.

H. DATA SAFETY MONITORING PLAN

H 1. Adverse events monitoring

[name], who is unaffiliated with the current study, has volunteered to serve as our data safety monitor (DSM). [name] is Professor and Vice Chair (Clinical Affairs) in the Department of Neurology here at Stony Brook. [name] will be unblinded to treatment. Assisted by study staff, she will periodically review the protocol documentation and safety data. The first review will occur after the first 5 subjects have been enrolled and on study drug for >6 weeks. Additional reviews will then take place quarterly. Among the important goals of the reviews will be to ensure that adverse events are reported, protocol amendments are filed with the IRB, inclusion/exclusion criteria are followed. If in the DSM's judgement a pattern of unexpected and clinically serious adverse events emerges, or if protocol compliance is inadequate, the study will be terminated.

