Any unfavorable and unintended symptom, sign (including a clinically significant abnormal laboratory finding) or disease that is temporally associated with a study will be considered a study AE. The study staff will carefully monitor each subject throughout the study for possible AEs, and document such in an AE log. Minimum information recorded for each AE includes type of event, duration (start and end dates), severity, seriousness, causality to study drug, action taken, and outcome. The PI or one of the Co-Is will grade the severity of AEs based on the DHHS/NIH Common Terminology Criteria for Adverse Events (CTCAE) v4.0. Baseline parkinsonian symptoms and signs documented prior to initiation of study medication will not be considered AEs. The PI will proactively bring to DSM attention any serious AEs judged possibly associated with study medication. Any unexpected fatal or life-threatening suspected adverse reactions will be reported to the FDA within 7 calendar days.

Table 6: Schedule for safety monitoring and assessments

	Assessments	Frequency
--	--------------------	------------------

H ₂ tablet and placebo	Stony Brook pharmacy will bottle tablets following USP 797 guidelines	At each preparation
Study safety	The Data Safety Monitor will review adverse events and protocol compliance	At the first 5 patients enrolled and on study drug > 6 weeks; proactive reviews will then take place quarterly

H 2. Data safety

All paper study data will be kept in secure, locked cabinets. All identifiable electronic study data will be password-protected and saved in Redcap and/or in a secure shared drive on the Stony Brook server only accessible by study staff. The study coordinator will check the data for accuracy. Missing data will be identified and obtained (if possible) in a timely fashion. Study staff will take steps to ensure that all information obtained is kept private. The subjects' names will not be used whenever possible. Study staff will instead use study codes lacking PHI. The electronic data will be banked on the same secure server after the study ends. The study staff may submit a new proposal to obtain approval from the IRB to use this data.

REFERENCES

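### The duty of prompt notice to the safety monitor covers only serious adverse events judged possibly related, so the others can wait about a quarter for the monitor's view of the cumulative pattern

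*Combined protocol and SAP*

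**What the plan says.** Section H 1 gives two routes by which an SAE reaches the DSM.

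- **Prompt route.** "The PI will proactively bring to DSM attention any serious AEs judged possibly associated with study medication". No time limit is stated, and the person who judges the association is not named. The PI is named as the notifier. The PI or a co-investigator is named for grading severity, but not for causality.
- **Scheduled route.** "The first review will occur after the first 5 subjects have been enrolled and on study drug for >6 weeks". After that, "Additional reviews will then take place quarterly". Table 6 describes the content: "The Data Safety Monitor will review adverse events and protocol compliance". Nothing there restricts the review by causality.

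Section H 1 says that the DSM "will be unblinded to treatment". Section D5.d says: "The study staff assessing study outcomes will remain blinded to treatment assignment".

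Section D7a defines safety as the absence of SAEs "warranting termination of the treatment arm or the trial, as determined by the Data and Safety Monitor", and section E repeats this. The termination rule in H 1 rests on the DSM's own judgement that a pattern of unexpected, clinically serious events has emerged. The analysis in section E is: "Safety will be assessed by comparing time to first SAE by log-rank tests". None of these three is limited to events attributed to study medication.

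**The concern.** A pattern is a property of events taken together. The prompt route selects events one at a time, by an opinion on each. If several hospitalisations each look like ordinary illness in subjects aged 40 to 80 with Parkinson's disease, each may be called unrelated, and only a comparison by arm would show otherwise. Pharmacy bottling is meant to keep study staff blinded (D6), so whoever among them judges causality should not be able to make that comparison. The DSM can, but is not owed notice of those events until the next scheduled review.

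What is at stake is how soon the DSM can judge whether the trial should stop, which is also the judgement on which the plan's definition of safety rests.

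**Working it through.** The plan states no figure on this point, so there is none to reproduce. The check has three parts.

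**1. Does any other route close the gap?**

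- FDA reporting within 7 calendar days (H 1) covers only unexpected fatal or life-threatening suspected reactions, and it goes to the FDA.
- IRB reporting (G 2) follows IRB guidelines and goes to the IRB.
- The adverse event log (H 1) records seriousness and causality for each event, but the DSM's access to it is described only through the periodic reviews.

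So an SAE not judged possibly associated has no required path to the DSM before the next scheduled review.

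**2. How long is the wait?**

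- After reviews have begun: one quarter = 52/4 = 13 weeks at most, with a mean of 13/2 = 6.5 weeks if events fall evenly.
- Before the first review: five subjects must be enrolled and on drug for more than 6 weeks. At uniform accrual of 70 subjects in 36 months (D8), with 4.345 weeks per month:
  - first subject at time zero: (4/70) × 36 + 6/4.345 = 2.06 + 1.38 = 3.4 months
  - first subject one accrual interval later: (5/70) × 36 + 6/4.345 = 2.57 + 1.38 = 4.0 months

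That is about 15 to 17 weeks, and more if early accrual is slow. An SAE soon after the first enrolment could therefore wait longer than a quarter.

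**3. How many events could be out of the DSM's sight at once?**

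Inputs from the documents: 70 subjects and 3 years of recruitment (D8), 52 weeks of treatment (D6). The SAE rate is an assumption, because the documents give none.

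- Subjects on drug at once, at steady state and ignoring drop-out: 70/3 × 1 = 23.3
- Person-years per quarter: 23.3 × 0.25 = 5.83
- Expected SAEs per quarter, both arms and any causality: m = 5.83 × rate
- Poisson probabilities: P(≥1) = 1 − e^(−m); P(≥2) = 1 − e^(−m)(1 + m)

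| Assumed rate per person-year | m | P(≥1) | P(≥2) |
|---|---|---|---|
| 5% | 0.29 | 25% | 3.5% |
| 10% | 0.58 | 44% | 12% |
| 20% | 1.17 | 69% | 33% |
| 30% | 1.75 | 83% | 52% |

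These counts are ceilings. SAEs judged possibly associated would be forwarded promptly, and the documents do not show what share that would be.

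As a yardstick for an imbalance, suppose k SAEs all fall in one arm under 1:1 allocation. The exact two-sided probability is 2 × 0.5^k, which is 0.0625 for k = 5 and 0.031 for k = 6. Six are needed to pass below 0.05. Six or more SAEs in a single quarter has probability below 1% at every rate in the table (0.9% at 30%).

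**The case against.** The strongest reply is that the scheduled review already does the work. It covers all adverse events, recurs quarterly and is done by an unblinded reviewer from a log that records seriousness and causality. The threshold for prompt notice, possible association, is low. The sentence sets a duty for some SAEs and does not forbid early notice of the rest. By the figures above, a decisive imbalance that arises and stays hidden within one quarter is remote. All of this stands, and it is why the point is small.

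It does not remove the mismatch. A pattern is cumulative, so one or two unseen events can matter when added to those already reviewed. The first review can also fall more than a quarter after the first enrolment.

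A reader might infer more than the documents support:

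- **That some SAEs never reach the DSM.** They do, at the next review. This is delay, not loss.
- **That the primary safety analysis is affected.** The log-rank test uses event dates and has no causality restriction. When the DSM hears of an event does not change it.
- **That termination depends on an investigator's attribution.** The rule is the DSM's own judgement and has no attribution condition. Attribution alters when the DSM sees an event, not whether it counts.
- **That the DSM is the only unblinded person.** The research pharmacist assigns treatment from the randomization list (D5.d). The DSM is the only unblinded safety reviewer described.
- **That the PI judges causality.** This is a reasonable inference, but the text does not say so.
- **That a given number of SAEs would be delayed.** That needs both an SAE rate and the share judged unrelated, and the documents give neither.

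**Conclusion.** The point holds as a minor one. The duty of prompt notice is narrower than the events on which the DSM must form a view, and no other route makes up the difference before the next review. The wait is up to about 13 weeks once reviews have begun, and about 15 to 17 weeks or more for an event at the very start of the trial. The first figure follows from the quarterly schedule. The second also assumes uniform accrual at the planned pace.

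The practical effect is small: about 0.3 to 1.75 SAEs of any causality per quarter over both arms, at assumed rates of 5% to 30% per person-year and steady-state exposure. The existence of the gap does not depend on those rates; only its weight does. The plan contains no miscalculation or contradiction here. This is a cheap improvement to a stated rule, with a modest gain in subject safety.

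**What to change.** Replace the sentence in H 1 with wording such as: *The PI will forward every serious AE to the DSM on becoming aware of it, regardless of judged relationship to study medication; the causality opinion accompanies the report.* It would help, in the same edit, to name the role that assigns causality and to set a time limit for forwarding.

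The cost is one changed sentence and a few extra messages to a monitor already in place, given the low number of SAEs likely. Treatment, sample size, the log-rank analysis and the quarterly reviews stay as they are.
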